3.3 DEFINITION OF END OF TRIAL

End of trial is defined as the last follow-up phone contact for the last patient. Patients with unresolved AEs at the last follow-up phone contact would be followed up until AE resolution or stabilisation.

4 STUDY PARTICIPANTS

4.1 INCLUSION CRITERIA

- 1. Informed consent
- 2. Patient-reported episode of acute diarrhoea defined as at least 3 watery stools within the last 48 hours
- 3. Aged 18 to 70

- 4. Willing and able to comply with the study protocol and evaluation(s) specified in the protocol
- 5. Considered suitable to take part in the study by the consenting nurse/GP (based on medical history and physical examination)

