3.2 STUDY OUTCOMES

3.2.1 Primary Outcome

Duration of diarrhoea defined as time (hours) from randomisation to first nonwatery stool (soft or firm)

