4.2 EXCLUSION CRITERIA

- 1. History of intestinal atony (severe constipation due to bowel obstruction)
- 2. Blood in stools
- 3. Any underlying condition that could cause chronic diarrhoea (such as gastroduodenal ulcer, ulcerative colitis, or Crohn's disease)
- 4. Patients with known cancer of any localisation
- 5. Use of any clinical trial investigational medication within the last 30 days before screening visit
- 6. Use of antibiotics since the onset of current diarrhoea episode
- 7. Pregnancy*
- 8. A history of clinically significant allergic reactions
- 9. Any underlying condition that could affect the patient's participation in this study or the results of this study in Investigator's opinion
- * Patient-reported; last menstrual period date will be recorded.

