4.3 PATIENT RECRUITMENT

Patients will be recruited to the study from an estimated 15 GP practices in the UK. GP practices are recruited to the study through the National Institute for Health Research (NIHR) Clinical Research Network (CRN).

Eligible patients will be identified opportunistically when patients contact their GP practice with symptoms of diarrhoea. The research GP or nurse can discuss the opportunity to take part in the trial by phoning the patient before the appointment, or during the appointment. The study can also be advertised to patients on practice notice boards with a poster and on practice websites and newsletters, and in newspapers, the Sponsor's website and social media accounts, public places and at local pharmacies using approved advertising materials, including the study poster in an electronic or printed format. Potentially eligible patients will be provided with the Patient Information Sheet. Patients who are interested to take part in the study after having had sufficient time to consider the information will be seen by the research GP or nurse at the practice to confirm eligibility. Informed consent will then be obtained by the GP or nurse before any study procedures are conducted.

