6 STUDY SCHEDULE AND PROCEDURES

Patients will complete 1 visit at their GP practice with 7 follow-up phone calls after the visit. The patients will not be invited for visits outside their standard of care regime. The schedule of visits/calls, and the procedures conducted and data collected at each visit/call are presented in **Table 1**. A +/- 2-day deviation is allowed for the Day 7 follow-up call.

Table 1. Schedule of procedures and data collection.

Procedure	Day 0 (Screening Visit)	Days 1- 7 (Follow-up calls)	End of study
Patient screening and consent	Х		
Demographic information and relevant medical history, symptoms and medication	x		
Randomisation	X		
Prescription for ORS (all patients) and provision of Enterosgel® (Interventional group)	Х		
Stool sample	X		
Other symptoms (vomiting, abdominal pain, nausea, fever etc)*	х	х	
Body temperature*		x	
Stool frequency and form*		х	
Medication use*		х	
Adverse Events*	 	x	
Returning of the diaries			х

^{*}Recorded by the patient in a patient diary from Day 0 (after randomisation) until end of Day 7 (**Appendix C**)

6.1.1 Day 0

On the Day 0 appointment, the patient's eligibility to take part in the study will be confirmed by the GP and written informed consent will be obtained by the GP or nurse before any study procedures take place. Screening will include a physical examination by the GP/nurse to ensure the patient is suitable to take part in the study (including measurement of body temperature, pulse and blood pressure).

The following information is then recorded in the eCRF:

- 1. Demographic information (age, gender, ethnicity)
- 2. Relevant medical history:
 - a) date of onset of symptoms (diarrhoea, vomiting, nausea, abdominal pain, fever etc.)
 - b) contact with suspected infection
 - c) details of travel
 - d) details of possible food poisoning
 - e) any antidiarrheal medication taken during the current episode

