The research nurse or GP will then randomise the patient to the intervention group using a computerised randomisation tool. Patients randomised to the Interventional group will be provided with a sufficient amount of Enterosgel® for 5-7 days of treatment and should take Enterosgel® as instructed in the study-specific instructions which will be provided to them (**Appendix A**). Patients randomised to the Control group will not receive any treatment in addition to the standard of care ORS treatment. The details of prescribed ORS treatment and any dietary recommendations will be recorded in the eCRF.

All patients will be provided with a patient diary (**Appendix C**) to record:

- 1. stool times and consistency
- 2. diarrhoea medication use
- 3. other symptoms (fever, nausea, vomiting etc.)
- 4. any AEs

Patients should fill in the patient diary daily from Day 0 until end of Day 7.

Patients will be asked to take a stool sample on the same day at home in a provided clean container. Patients in the Interventional Group should take the stool sample before taking the first Enterosgel® dose. ORS treatment can be started before taking the stool sample. The sample should be taken to the medical practice by the patient or a family member/friend. It will then be delivered to a local laboratory to test for the presence of rotavirus and diarrhoea causing bacteria (i.e.

Campylobacter, Clostridium difficile, Escherichia coli, Salmonella enterica, Shigella), in order to identify the likely cause of the episode. If there is a reason to suspect norovirus infection (i.e. outbreak), this will also be tested for. Patients who have recently travelled abroad will be additionally tested for *Pseudomonas* and *Vibrio cholerae*. A stool sample will only be collected in baseline and the results will be summarised in baseline characteristics.

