15 APPENDICES

APPENDIX A: ENTEROSGEL® STUDY USE INSTRUCTIONS

Randomised, multi-centre study to assess efficacy, tolerability and safety of Enterosgel® in treatment of acute diarrhoea in adults

Enterosgel® use instructions for research participants

IMPORTANT:

- Stop taking Enterosgel® if you did not have any bowel movements for 2 days at any stage of the study
- Mix every dose of Enterosgel® in 100-200 ml of room temperature water
- Please leave at least 1 hour between taking Enterosgel® and any other medication or meals

Day 0 (today):

First dose (as soon as possible): 2 tablespoons or 2 sachets of Enterosgel®

After the first dose: 1 tablespoon or 1 sachet of Enterosgel® after every bowel movement up to a total of 6 times and at least 3 times a day

Day 1:

If you have loose stool more than once a day:

1 tablespoon or 1 sachet of Enterosgel® after every bowel movement up to a total of 6 times and at least 3 times a day

If you don't have loose stool or have it just once a day:

1 tablespoon or 1 sachet of Enterosgel® 3 times a day

Days 2, 3, 4 and 5:

If you have loose stool more than once a day:

1 tablespoon or 1 sachet of Enterosgel® 3 times a day

If you don't have loose stool or have it just once a day:

1 tablespoon or 1 sachet of Enterosgel® 1-2 times a day

Days 6 and 7:

If you have loose stool more than once a day:

1 tablespoon or 1 sachet of Enterosgel® 3 times a day

If you don't have loose stool or have it just once a day:

Stop taking Enterosgel®

ENT02UK

Enterosgel® use instructions v.1.0

12/10/2016

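### Inclusion criterion 2 does not require the last stool before randomisation to be watery, so a patient who has already met the primary endpoint's recovery event can be randomised

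*Protocol*

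**What the plan says.** **Entry.** Protocol section 4.1, item 2, requires a "Patient-reported episode of acute diarrhoea defined as at least 3 watery stools within the last 48 hours". Neither the other inclusion criteria nor the exclusions in section 4.2 say what the latest stool before randomisation must look like.

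**Primary outcome.** Section 3.2.1: "Duration of diarrhoea defined as time (hours) from randomisation to first nonwatery stool (soft or firm"). The clock starts at randomisation and stops at the first stool of either form.

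**Text that presumes ongoing illness.** Section 4.1, item 5, asks that the patient be "Considered suitable to take part in the study by the consenting nurse/GP (based on medical history and physical examination"). Exclusion 6 in section 4.2 reads "Use of antibiotics since the onset of current diarrhoea episode". Section 4.3 says "Eligible patients will be identified opportunistically when patients contact their GP practice with symptoms of diarrhoea".

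**Day 0 data.** The history list in section 6.1.1 includes the "date of onset of symptoms (diarrhoea, vomiting, nausea, abdominal pain, fever etc".), but not the time or form of the last stool. The diary starts only after randomisation.

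**Power.** Section 8.1 assumes an SD of 1.3 days and a mean reduction of 1 day. It arrives at 36 per group for 90% power at the 5% level, 52 per group after 30% losses, and 104 in total.

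**The concern.** The entry rule looks back over 48 hours, while the endpoint looks forward from randomisation. Both rest on stool form, but nothing links them. Take a patient with three watery stools on the day before the visit and a soft stool that evening. This patient satisfies criterion 2, yet the event that defines the end of diarrhoea under section 3.2.1 has already happened. What is then recorded as duration is, in the ordinary case, the interval to the next stool.

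That interval carries little or no information about whether the product shortens diarrhoea. Such patients add short values to both arms and pull the mean difference towards zero. They also count as resolved by Day 3 (secondary outcome 2) in both arms. Because the Day 0 list does not capture the last stool, they could not be reliably identified afterwards and set aside in a sensitivity analysis.

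**Working it through.** **1. Is there a safeguard elsewhere in the protocol?**
- Item 5 of section 4.1 is a general suitability judgement. It does not ask whether diarrhoea is still present.
- The word 'current' in exclusion 6 fixes the time window for antibiotic use. It is not an entry condition of its own.
- The recruitment text in section 4.3 describes symptoms at first contact with the practice, not at randomisation. The same section allows recruitment through posters, newspapers and social media, and gives patients time to consider the information before they are seen. Section 1 says the illness usually resolves within days without treatment. Recovery between first contact and randomisation is therefore possible.

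None of these closes the gap.

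**2. Reproduce the plan's figure.** Inputs from section 8.1: difference 1 day, SD 1.3 days, 5% level (two-sided; a one-sided test would give 29), power 90%.

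n per arm = 2 × 1.3² × (1.960 + 1.282)² / 1² = 35.5, rounded up to 36.

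With 30% losses: 36 / 0.7 = 51.4, rounded up to 52 per arm, so 104 in total. The plan's figures are confirmed. Power at 36 per arm is 90.4% by the normal approximation and 89.6% by the t-test (70 degrees of freedom).

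**3. Effect of a share f of entrants who had already passed a soft or firm stool.** Assumptions, none of them stated in the protocol:
- f is the same in both arms;
- these patients have the same expected wait in both arms;
- the 1-day effect applies to the remaining patients only;
- the SD stays at 1.3 days.

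The expected difference is then (1 − f) × 1 day. The standard error is 1.3 × √(2/36) = 0.3064 days, and the noncentrality is (1 − f) / 0.3064.

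| Assumed f | Difference (days) | Noncentrality | t-test power |
|---|---|---|---|
| 0% | 1.00 | 3.264 | 89.6% |
| 5% | 0.95 | 3.100 | 86.4% |
| 10% | 0.90 | 2.937 | 82.6% |
| 20% | 0.80 | 2.611 | 73.1% |
| 30% | 0.70 | 2.284 | 61.5% |

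**4. Sensitivity to the fixed SD.** Mixing two kinds of patient also changes the SD. For each arm, variance = (1 − f)(1.3² + m²) + f(s² + w²) − [(1 − f)m + fw]². Here m is the mean duration in patients with ongoing diarrhoea, and w and s are the mean and SD of the wait in the others.

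Take w = 0.5 day, s = 0.4 day, f = 20%, and m = 3 days in control against 2 days in intervention (all assumed).
- Control: 0.8 × (1.69 + 9) + 0.2 × (0.16 + 0.25) − 2.5² = 2.384.
- Intervention: 0.8 × (1.69 + 4) + 0.2 × (0.16 + 0.25) − 1.7² = 1.744.
- Pooled SD = √[(2.384 + 1.744) / 2] = 1.44, and power is 65.6% (normal approximation).

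Letting the control mean run from 2 to 4 days gives 84% to 70% at f = 10%, 77% to 52% at 20%, and 68% to 39% at 30%. The direction is the same throughout, but the size depends heavily on inputs the protocol does not give.

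**The case against.** The strongest reply is that the share may be small. Most patients are found because they report diarrhoea to their practice, and a nurse or GP takes a history before enrolling them. At 5% the loss is about three percentage points of power. This stands: nothing in the protocol supports 10% to 30%, and the table shows a range, not a forecast.

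Second, section 8.1 states the 1-day reduction as an average between the randomised groups. If the sponsor meant it to cover every entrant, recovered or not, it already contains the dilution and the discount does not apply. This also stands as a limit on the figures, though section 8.1 does not say that any such allowance was made.

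Third, a patient who has passed one soft stool may relapse, and the next stool may be watery. Such a patient is not wholly uninformative, so the claim is about what normally happens.

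A reader might infer more than this. Four such readings are not supported.
- *That a patient with no stool at all since the last watery one has already recovered.* Under section 3.2.1 recovery needs a soft or firm stool, so this patient is unresolved.
- *That Appendix A defines diarrhoea differently from criterion 2.* Its branch beginning "If you don't have loose stool or have it just once a day" first appears on Day 1 and is a use instruction for patients already enrolled. It does not define the condition.
- *That the Day 0 sample rule, "Patients in the Interventional Group should take the stool sample before taking the first Enterosgel® dose", is part of the same defect.* A pre-dose soft stool can occur in a patient whose previous stool was watery. That is a separate matter, which a change to criterion 2 would not resolve.
- *That the gap could produce a false positive.* Allocation is 1:1 and stratified by site, so such entrants should be balanced between arms. The expected effect is towards no difference.

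**Conclusion.** The gap in the wording is certain: criterion 2 lets in patients for whom the event ending the primary outcome has already occurred, and the listed Day 0 data would not reliably show who they are. Its practical weight is uncertain, because the number of such patients is unknown. Under the stated assumptions the cost runs from about 3 points of power at a 5% share to about 28 points at 30% (89.6% − 61.5%).

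This does not show that the trial is underpowered or that its result would be biased in favour of the product. It is a cheap improvement to the entry rule that aligns it with the endpoint.

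**What to change.** Add to criterion 2 in section 4.1: *and the most recent stool before randomisation was watery*. Add two fields to the Day 0 eCRF list in section 6.1.1, for the time and the form of that stool.

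This single clause is enough. A further condition that no soft or firm stool has followed would be redundant. A requirement for a watery stool within 24 hours would shut out patients who are still unresolved under section 3.2.1.

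The cost is a short amendment, two eCRF fields and one question at a visit that already takes place. A few patients who are already recovering will not be enrolled, so recruitment will be slightly slower; if the share turned out to be large, so would that cost. The figures of 36, 52 and 104 stay as they are.

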4.2 EXCLUSION CRITERIA

- 1. History of intestinal atony (severe constipation due to bowel obstruction)
- 2. Blood in stools
- 3. Any underlying condition that could cause chronic diarrhoea (such as gastroduodenal ulcer, ulcerative colitis, or Crohn's disease)
- 4. Patients with known cancer of any localisation
- 5. Use of any clinical trial investigational medication within the last 30 days before screening visit
- 6. Use of antibiotics since the onset of current diarrhoea episode
- 7. Pregnancy*
- 8. A history of clinically significant allergic reactions
- 9. Any underlying condition that could affect the patient's participation in this study or the results of this study in Investigator's opinion
- * Patient-reported; last menstrual period date will be recorded.

4.3 PATIENT RECRUITMENT

Patients will be recruited to the study from an estimated 15 GP practices in the UK. GP practices are recruited to the study through the National Institute for Health Research (NIHR) Clinical Research Network (CRN).

Eligible patients will be identified opportunistically when patients contact their GP practice with symptoms of diarrhoea. The research GP or nurse can discuss the opportunity to take part in the trial by phoning the patient before the appointment, or during the appointment. The study can also be advertised to patients on practice notice boards with a poster and on practice websites and newsletters, and in newspapers, the Sponsor's website and social media accounts, public places and at local pharmacies using approved advertising materials, including the study poster in an electronic or printed format. Potentially eligible patients will be provided with the Patient Information Sheet. Patients who are interested to take part in the study after having had sufficient time to consider the information will be seen by the research GP or nurse at the practice to confirm eligibility. Informed consent will then be obtained by the GP or nurse before any study procedures are conducted.

4.4 WITHDRAWAL CRITERIA

Patients can withdraw consent at any time without providing a reason. No further

data will be collected after a patient withdraws consent or is withdrawn from the study, but data collected before withdrawal can be used.

In case of the following the patient should be withdrawn from the study:

- 1. Refusal to continue the use study treatments
- 2. Significant deterioration of the patient's status
- 3. Serious Adverse Event (SAE)
- 4. Serious adverse reaction
- 5. Changes in diagnosis
- 6. Major protocol violation (affecting patient safety and/or scientific quality of the data)

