8.3 ANALYSIS POPULATIONS

8.3.1 Intention-to-treat population (ITT)

ITT population will include all randomised patients analysed in the groups to which they were randomised to, regardless of whether they received or adhered to the allocated intervention.

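### Section 4.4 ends data collection for patients who refuse treatment or get worse, which conflicts with the intention-to-treat primary analysis

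*Protocol*

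**What the plan says.** Protocol section 4.4 sets one rule for two different situations. It states that no further "data will be collected after a patient withdraws consent or is withdrawn from the study, but data collected before withdrawal can be used". It then says: "In case of the following the patient should be withdrawn from the study". Six items follow:

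- item 1: "Refusal to continue the use study treatments"
- item 2: "Significant deterioration of the patient's status"
- item 3: a serious adverse event (SAE)
- item 4: a serious adverse reaction
- item 5: "Changes in diagnosis"
- item 6: a major protocol violation

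Nothing in the section separates stopping treatment from leaving the study.

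Section 8.2 makes the primary analysis intention-to-treat. Section 8.3.1 defines that set as everyone randomised, in the group assigned, "regardless of whether they received or adhered to the allocated intervention". Section 3.2 measures the primary outcome from randomisation to the first soft or firm stool and names the patient diary as the source for every efficacy outcome. Section 3.3 adds: "Patients with unresolved AEs at the last follow-up phone contact would be followed up until AE resolution or stabilisation".

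**The concern.** An analysis that disregards adherence needs outcomes from patients who do not adhere. Section 4.4 treats refusal of treatment as a reason to stop collecting them, and does the same for patients whose condition worsens. Both events are more likely while diarrhoea persists, so the missing durations would tend to be the long ones.

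The loss may also be unequal between arms. The trial is open-label, both arms are prescribed oral rehydration solution, and only the Interventional arm has the gel as well. Section 9.3 lists never using the gel, in patients randomised to it, among its examples of protocol violations. Whether that counts as major under item 6 of section 4.4 is not stated.

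If losses concentrate among long durations in one arm, the comparison of mean durations is biased. A statistical analysis plan can choose a missing-data method, but it cannot recover diary entries that sites were told not to collect.

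**Working it through.** **1. The sections side by side.** Take a patient who refuses further treatment on Day 2 while every stool so far has been watery.

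- Section 8.3.1: the patient stays in the primary analysis set.
- Section 4.4: the patient should be withdrawn, and the diary and calls stop.
- Section 3.2.1: no soft or firm stool has been recorded, so the primary outcome is unobserved.

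A patient who had already passed a soft or firm stool keeps the primary outcome. Such a patient can still lose the time to last watery stool and the symptom durations, which need later diary entries.

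**2. The protocol's own sample size.** Inputs from section 8.1: difference 1 day, SD 1.3 days, 90% power, 5% significance (two-sided reproduces the figure).

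- n per arm = 2 × 1.3² × (1.960 + 1.282)² / 1² = 35.5, rounded up to 36.
- Inflated for 30% withdrawal and missing data: 36 / 0.70 = 51.4, rounded up to 52 per arm, 104 in total.

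Both figures reproduce. The 30% allowance restores precision only; it does nothing about bias from outcome-related loss.

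**3. Illustration of size, with no true effect.** Gamma durations, SD 1.3 days (protocol), mean 3 days (assumed), 52 per arm. A patient with duration T is lost with probability 1 − (1 − h)^floor(T), where h is the assumed chance of refusal per ill day. For h = 0.05 this is 1 − 0.95 = 5% at T = 1.5 days and 1 − 0.95⁶ = 26% at T = 6.2 days, so long durations are lost more often. The analysis is a t-test on the patients left (assumed, since section 8.2 leaves the missing-data method open).

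| Refusal per ill day, Interventional / control | Spurious benefit of the gel (days) | Type I error (nominal 5%) |
|---|---|---|
| 5% / 0 | 0.09 | 6–7% |
| 10% / 0 | 0.17 | 9% |
| 5% / 2.5% | 0.04 | 5–6% |
| 10% / 5% | 0.08 | 6% |
| equal rates | about 0 | about 5% |

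In the first two rows about 12% and 22% of the Interventional arm are withdrawn. By symmetry, swapping the arms in any row reverses the sign: 5% / 10% gives −0.08 day.

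**4. An outer bound.** Suppose that exactly the longest fraction q of normally distributed durations is lost in one arm. The mean then shifts by 1.3 × φ(z) / (1 − q), where z is the upper-q normal quantile. For q = 10% this is 1.3 × 0.1755 / 0.90 = 0.25 day. It favours the gel if the Interventional arm loses them and favours control if control does. This is a worst case, not an expectation.

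**The case against.** Several points on the other side stand.

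- **The analysis remains possible.** A reader might infer that the intention-to-treat analysis cannot be done at all. The documents do not support that. Section 8.3.1 defines who is analysed, data gathered before withdrawal are kept, and patients resolved by then have their primary outcome. The rest could be censored or imputed, although under assumptions that cannot be tested. Section 8.2 commits to reporting reasons for missing data and to sensitivity analyses.
- **The trigger is narrower than stopping treatment.** Section 4.4 says should, not must, and names refusal. A patient who stops because Appendix A says so has not refused.
- **Hospitalisation.** It is tempting to argue that secondary outcome 5 is lost because hospitalisation can be an SAE and so a withdrawal trigger. A hospitalised patient has already met that outcome, and section 6.1.3 has the event recorded.
- **Changed diagnosis.** One might link item 5 to the stool result. Section 6.1.1 only says that stool results are summarised at baseline; it ties them to no withdrawal.
- **Adverse-event follow-up.** One might read section 4.4 as plainly forbidding what section 3.3 promises. For a withdrawn patient the last phone contact could be the one at withdrawal, and section 7.2 requires SAE reporting in any case. The two sections are unreconciled; neither clearly overrides the other.
- **Direction.** Controls can refuse rehydration solution, and items 2 to 5 apply to both arms. A bias in favour of the gel is plausible but not established.

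What remains is a stated rule that stops collection of data the primary analysis needs. No later choice of method restores those data.

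**Conclusion.** The conflict between section 4.4 and sections 8.2 and 8.3.1 is real and rests on the text alone. Intention-to-treat is compromised, not impossible: unresolved patients who are withdrawn contribute no observed primary outcome, for reasons plausibly tied to that outcome.

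The size is uncertain. With the protocol's SD, refusal confined to the Interventional arm produces at most 0.17 day in the scenarios simulated, about one sixth of the 1-day target (0.17 / 1). The bias halves if controls refuse at half the rate, vanishes at equal rates, and reverses if control loses more. The figures depend on the assumed 3-day mean, the assumed refusal rates and a complete-case t-test. A larger bias, such as a third of the target, would need a larger SD than the protocol assumes together with no control losses, and the documents support neither.

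**What to change.** Separate stopping study treatment from leaving the study.

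- In section 4.4, limit the bar on further data to patients who withdraw consent to follow-up.
- For items 1 to 6, continue the diary and daily calls to the end of Day 7 unless the patient declines.
- Reconcile section 4.4 with sections 3.3, 8.2 and 8.3.1, so that adverse-event follow-up and the analysis set agree with it.

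This changes data collection only. When treatment should stop is left as it is.

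The cost is protocol wording, matching patient-information wording where needed, and a few more calls to patients off treatment. The diary and calls already exist, and no larger sample is needed. If all 52 per arm were observed, power under the protocol's assumptions would be about 97%, against about 90% with 36.
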